***Non-parametric tests:***

Below are potential types of comparisons with relevant criteria:

1. To evaluate difference in continuous variables obtained in two different (independent) groups – Mann-Whitney test.
2. To evaluate time changes in the parameters compared – Friedman test, nonparametric analogue of repeated measures analysis of variance.
3. For frequency analysis of contingency tables  $2 \times 2$  –  $\chi^2$  (if the frequency under comparison  $> 5$ ) or exact Fisher’s test (if one of the frequencies under comparison  $< 5$ ).
4. Cochran-Mantel-Haenszel test (modified  $\chi^2$  test for multiple comparisons) – to perform frequency analysis based on independent strata.
5. For frequency analysis of data on presence/absence of an event or outcome during repeated measurements (contingency tables with dependent strata) – survival analysis.

To perform the above-mentioned nonparametric statistical analysis the following SAS procedures are to be used:

- FREQ – Friedman test,  $\chi^2$  test and/or exact Fisher's test; Cochran-Mantel-Haenszel test.
- LIFETEST – survival analysis.
- NPAR1WAY - Mann-Whitney test.

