### *Secondary Outcome Measures*

2. Fever changes over time (body temperature change on days 2-7 compared to baseline).
3. Average duration of fever.
4. Proportion of subjects with normal body temperature (below 37,0^0C) on days 2-7.
5. Severity of clinical manifestations of influenza (fever, general symptoms and nasal/throat/chest symptoms) in scores on day 1-7 – according to the patient's diary; on days 1, 3 and 7 – according to objective examination by the investigator.

---

 **Recovery criteria:** body temperature <37.0^0C + no symptoms.

**Improvement criteria:** body temperature ≤37.2C + total symptom score (except for fever index) ≤2 scores.

 Criteria of no fever - body temperature lower than 37.0° C for 24 hours.

6. Duration of the major clinical symptoms of influenza (fever, general symptoms and (nasal/throat/chest symptoms) in days (according to the patient diary).
7. Severity of influenza course (based on area under curve for total influenza severity score on days 1-7 – according to the patient diary; on days 1, 3 and 7 – according to objective examination by the physician).
8. Proportion of patients, who used antipyretics on days 1, 2, 3, 4 and 5 of the treatment.
9. Proportion of patients with complications requiring antibiotics, aggravation of the disease (severe influenza).
10. Proportion of patients with negative results of virology assay on days 3, 5 and 7 (based on PCR of nasopharyngeal swabs).
11. Dynamics of Parameters of Immune Status (T-cell and B-cell Immune Response) on days 1, 3 and 7 of the observation:
  - Concentration of regulators of the T-cell immune response (IL2, IFN  $\gamma$ , IL-18), and regulators of B-cell immune response (IL-4, IL-16).
12. Dynamics of Parameters of Immune Status ( IFN- $\alpha$  and IFN- $\gamma$  Production) on days 1, 3 and 7 of the observation:
  - Level of spontaneous and induced production of IFN- $\alpha$  and IFN- $\gamma$  by leukocytes (in vitro).
13. Dynamics of Parameters of Immune Status (Absolute Number of Each Type of White Blood Cells and Different Lymphocyte Phenotypes) on days 1, 3 and 7 of the observation:
  - The absolute number of each type of white blood cells (WBC): Absolut Count (AC) of leukocytes, neutrophils, lymphocytes, monocytes, eosinophils, basophils, and CD3, CD4, CD8, CD4/CD8, CD16, CD119 leukocytes.

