### Study design scheme

### Schedule of study procedures

Procedure/visit	Day 1	Day 3	Day 5	Day 7
Obtaining informed consent (signing informed consent by the patient)	+			
Collection of complaints	+	+		+
Collection of medical history data	+			
Objective examination	+	+		+
Recording influenza symptoms in scores	+	+		+
Collection of nasal swabs and isolation of influenza agent antigens	+			
Collection of nasopharyngeal swab for PCR diagnosis	+	+	+	+
Pregnancy test	+			
Information on concomitant medicines	+	+		+

Inclusion/exclusion criteria	+			
Randomization and prescription of study therapy	+			
Antipyretic drug dispensing	+			
Blood sampling for immunological tests	+	+		+
Dispensing of the study drug	+			
Drug accountability and return, assessment of compliance				+
Distribution of diaries	+			
Evaluation of correct diary filling		+		+
Diary return				+
Evaluation of therapeutic safety		+		+

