### *Evaluation of sample size*

The sample size was assessed in accordance with the following rules and assumptions:

1. Statistical assumptions:

- 1.1 Lack of clinically relevant superiority of reference product (oseltamivir) over test product (Ergoferon) is assumed, thus statistically meeting Non-Inferiority design:

$$\mathbf{H_0: Ef_{control} - Ef_{test} \geq \delta}$$

$$\mathbf{H_A: Ef_{control} - Ef_{test} < \delta,}$$

where  $\mathbf{Ef_{control}}$  – effect of reference product (oseltamivir),  $\mathbf{Ef_{test}}$  – effect of test product (Ergoferon),  $\delta$  – clinically relevant difference;

- 1.2 Clinically relevant difference value “ $\delta$ ” is considered to be equal to 20% (i.e. Ergoferon effect is supposed to be comparable to the one of oseltamivir if the effect of test product is superior to or inferior to the effect of reference product by no more than 20%);
- 1.3 The power of statistical tests ' $P = (1 - \beta)$ ' is 80% (the probability of correct rejection of the null hypothesis is 0.8);
- 1.4 The probability of type 1 error ' $\alpha$ ' is less than 5% (the probability of false acceptance of the alternative hypothesis is less than 0.05);
- 1.5 Therefore, sample size will be calculated taking into account:
- a. assumption on expected effects declared in the main efficacy criterion of the protocol;
- 1.6 calculation of sample size of groups 1 and 2 for two-sided test for final analysis will be made using the formula:

$$\mathbf{N_1=N_2=(p_a(1 - p_a) + p_b(1 - p_b)) I,}$$

where  $\mathbf{N_1}$  and  $\mathbf{N_2}$  – samples sizes in Ergoferon and Oseltamivir groups

$\mathbf{p_a}$  and  $\mathbf{p_b}$  – expected proportions of the patients with recovery/improvement in these groups

$\mathbf{I}$  – Fisher's information detected using the formula:

$$\mathbf{I=(z_\alpha + z_\beta)^2/(\theta - \delta)^2,}$$

where  $\mathbf{z_\alpha}$  and  $\mathbf{z_\beta}$  – tabular values of z-test for  $\alpha$  and  $\beta$ ,  $\theta$  – difference between proportions ( $\mathbf{p_a - p_b}$ ),  $\delta$  – clinically relevant difference;

- 1.7 final sample size will be determined using the formula:

$$\mathbf{N_F = N / (1 - K_B),}$$

---

 SAS/STAT(R) 9.2 User's Guide, Second Edition.

[http://support.sas.com/documentation/cdl/en/statug/63033/HTML/default/viewer.htm#statug\\_seqdesign sect027.htm](http://support.sas.com/documentation/cdl/en/statug/63033/HTML/default/viewer.htm#statug_seqdesign sect027.htm)

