**Parametric criteria**

Prior to analysis using parametric statistics, data samples under comparison will be tested for normality (the Kolmogorov-Smirnov test).

 **Recovery criteria:** body temperature  $<37.0^{\circ}\text{C}$  + no symptoms.

**Improvement criteria:** body temperature  $\leq 37.2^{\circ}\text{C}$  + total symptom score (except for fever index)  $\leq 2$  scores.

The following parameters and approaches are to be used:

1. To evaluate the differences in continuous variables from two different (independent) groups – Student’s test for independent samples.
2. To evaluate differences in continuous variables in one group at two different visits - Student’s test for paired samples.
3. To evaluate time changes in parameters compared - analysis of variance (ANOVA) or modified repeated measures covariance (ANCOVA).
4. In case of multiple comparisons of the groups various corrections for multiplicity will be used, e.g. Dunnett, Tukey, Scheffe, Holm adapted test, etc.
5. In case of abnormal data distribution generalized linear models and/or mixed linear models will be used.
6. Selection of the type of distribution, specification of factor and covariance structures of the model will be made using fit-statistics such as AIC (Akaike information criterion).

The following SAS software programs are supposed to be applied to the above listed tests and techniques:

- UNIVARIATE: normality verification of the distributions under comparison
- CORR, MEANS - calculation of descriptive statistics
- TTEST – Student’s test with all modifications
- GLM – generalized linear models for analysis of time changes (ANOVA, ANCOVA)
- GENMOD – generalized linear models
- MIXED – mixed linear models.

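### No baseline adjustment is pre-specified for the primary recovery/improvement proportion, and the plan does not say when, or with which covariate, continuous outcomes are adjusted

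*Combined protocol and SAP*

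**What the plan says.** **Primary outcome.** It is the proportion with recovery or improvement on days 2–7 (diary) and on days 3 and 7 (examination). Both states are defined by a temperature limit together with absent or low symptoms. Statistical criteria places comparisons of proportions in the non-parametric group. Under Non-parametric tests, which is introduced as a list of potential comparisons, item 3 reads "For frequency analysis of contingency tables" of 2×2 form and names chi-square or Fisher's exact test. Item 4 adds Cochran-Mantel-Haenszel over independent strata but names no stratum. Item 5 offers survival analysis for events assessed repeatedly.

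**Continuous outcomes.** Parametric criteria, item 1 ("To evaluate the differences in continuous variables from two different (independent) groups") gives Student's test, and the non-parametric list gives Mann-Whitney. Item 3 of Parametric criteria gives ANOVA or a repeated-measures ANCOVA for changes over time, with no covariate named. Item 5 brings in generalised or mixed models when data are not normal. Item 6 leaves the choice of model factors to fit statistics such as AIC. Secondary outcome 2 is "body temperature change on days 2-7 compared to baseline".

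**Baseline data.** Inclusion criterion 3 requires a temperature of at least 37.8 °C and a symptom score of at least 4. The Schedule of study procedures has "Recording influenza symptoms in scores" on Day 1. Inclusion criterion 2 requires presentation within 48 hours of onset, but no schedule item records the time of onset.

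**The concern.** Recovery/improvement is a threshold on temperature and symptom score. Entry sets a floor on both but no numerical ceiling, so patients can start at quite different distances from that threshold. Day 1 values are therefore natural prognostic covariates. A standardised risk difference that uses them estimates the same quantity as the unadjusted one, usually with a narrower interval, and it corrects for chance imbalance. In a non-inferiority comparison the width of the interval relative to the margin decides the result.

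There is also a question of pre-specification. The plan lists several methods that could adjust, but names no covariates or strata and lets model factors be chosen on fit. In an open-label trial that leaves the choice of adjustment open until outcome data have been seen.

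**Working it through.** **Inputs from Evaluation of sample size**
- Margin: δ "is considered to be equal to 20" per cent, read here as percentage points.
- Power: "the probability of correct rejection of the null hypothesis is 0.8".
- Type I error: "the probability of false acceptance of the alternative hypothesis is less than 0.05".
- Sidedness: the hypotheses are one-sided, yet the text says "calculation of sample size of groups 1 and 2 for two-sided test for final analysis will be made using the formula". So z_α may be 1.645 or 1.96.
- True difference: θ = 0, the lower end of the stated expectation.
- Size: 79 per arm, 158 in total, 198 consents.

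**Not in the documents:** the response rates p and the share of outcome variation explained by baseline (R²). Both are assumptions below.

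**Step 1. Reproduce 79.** The plan's formula with equal rates is N = 2p(1−p)(z_α + z_β)²/δ², with z_β = 0.842.
- One-sided 5%, p = 0.50: 0.50 × (1.645 + 0.842)²/0.04 = 77.3, so 78.
- Two-sided 5%, p = 0.72: 0.4032 × (1.96 + 0.842)²/0.04 = 79.1, so 80. Exactly 79 results for p of about 0.721–0.726.
- Two-sided 5%, p = 0.50: 98.1, so 99. This does not match.

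The consent figure follows: 158/(1 − 0.20) = 197.5, so 198. Because p is unstated, 79 can only be solved backwards, and the first two readings fit.

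**Step 2. Unadjusted power at 79 per arm.** SE = √(2p(1−p)/79); power = Φ(0.20/SE − z_α).
- p = 0.50, z_α = 1.645: SE = 0.0796; Φ(2.514 − 1.645) = 80.8%.
- p = 0.72, z_α = 1.96: SE = 0.0714; Φ(2.800 − 1.960) = 79.9%.

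**Step 3. With adjustment.** Multiply the variance by (1 − R²).

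| R² (assumed) | Power, one-sided 5%, p = 0.50 | Power, two-sided 5%, p = 0.72 | n per arm for 80% power (same order) |
|---|---|---|---|
| 0 | 80.8% | 79.9% | 78; 80 |
| 0.05 | 82.5% | 81.9% | 74; 76 |
| 0.10 | 84.3% | 83.9% | 70; 72 |
| 0.20 | 87.8% | 87.9% | 62; 64 |

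**Step 4. Check the (1 − R²) factor.** Trials with 79 per arm were simulated (1,500 per setting, logistic outcome, one normal baseline covariate, p = 0.50 and 0.72). The variance of the standardised risk difference divided by that of the unadjusted one was 0.95–0.97 at R² of about 0.05, 0.88–0.91 at about 0.11–0.12, and 0.78–0.81 at about 0.20–0.22. The factor is a fair guide.

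**Step 5. Continuous outcomes.** Relative to an unadjusted test on the follow-up value, ANCOVA has variance factor 1 − ρ², where ρ is the correlation of baseline with follow-up: 0.91 at ρ = 0.3 and 0.75 at ρ = 0.5. The documents give no ρ.

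**The case against.** The strongest reply is that adjustment is left open, not ruled out: Cochran-Mantel-Haenszel, ANCOVA, generalised and mixed models all appear, and survival analysis could serve an outcome assessed on several days. That is correct, and it limits the point to missing pre-specification. It does not fill the gap, since none of these methods is tied to the primary proportion and none has a named covariate or stratum.

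Three stronger readings are tempting, and the documents do not support them.

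- *Temperature change will be analysed by a t test on change scores, wasting 25–35% of variance.* No section assigns that test to this outcome, and the ANOVA/ANCOVA item for changes over time fits it at least as well. The percentages also assume equal SDs: 2(1−ρ) against 1−ρ² is 1.40 against 0.91 at ρ = 0.3, and 1.00 against 0.75 at ρ = 0.5. If the baseline SD were half the follow-up SD, change-score variance would be 1.25 − ρ, that is 0.95 against 0.91 (about 4%) and 0.75 against 0.75 (none).
- *The trial has only about 71% power.* That needs two-sided 5% with p = 0.50, a pairing for which the plan's formula asks for 99 per arm, so it cannot be the source of 79. At two-sided 5% and p = 0.80, power is 88.1%; at one-sided 5% it is at least 80.8% for every p.
- *Hours since onset are available as a covariate.* Only the 48-hour limit is stated.

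It is also fair that the entry limits truncate the covariates, which may lower R², and that a logistic model may be unstable on days with few events. Both stand, and the fix allows for the second.

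**Conclusion.** The point holds as a gap in pre-specification with a cost in precision. No baseline covariate or stratum is fixed for the primary outcome. For continuous outcomes, unadjusted tests and ANOVA/ANCOVA stand side by side with no rule for which applies and no mention of the Day 1 value as covariate.

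The size is conditional. At the two readings that fit 79 per arm, the design sits at its 80% target with almost no reserve, and adjustment would add about 2 points of power at R² = 0.05 and about 7 to 8 at R² = 0.20. This rests on θ = 0, a margin in percentage points, and assumed values of p and R². If the true rates are well above those values, power is already higher and the gain matters less.

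A reader might infer that the unadjusted comparison is biased or invalid. It is neither: under randomisation, leaving out covariates loses precision only.

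**What to change.** State in the SAP:

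1. **Primary outcome.** At each primary time point, fit a logistic model with arm, Day 1 temperature and Day 1 total symptom score, fixed in advance, including which Day 1 source (diary or examination) supplies the score. Obtain the risk difference and its confidence interval by standardisation and compare that interval with the 20-point margin. Add time since onset only if it is confirmed to be recorded.
2. **Sensitivity and fallback.** Report the unadjusted risk difference and interval throughout. Use it as the main result at any time point with too few events to fit the model, by a rule written down beforehand.
3. **Continuous outcomes with a Day 1 measurement.** Use ANCOVA on the follow-up value with its own Day 1 value as covariate. Outcomes without a Day 1 value, such as duration of fever, are not covered.
4. **Model choice.** Remove selection of covariates by AIC for these analyses.

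The interval in item 1 is needed anyway, because chi-square and Fisher tests as listed test equality and not the non-inferiority hypothesis. Which time point carries the primary conclusion is a separate matter that this change does not settle.

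Cost: SAP wording and a few lines of code. Temperature and symptom score are already obtained on Day 1, so no patients or visits are added; onset time needs a check of the case report form.

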### ***Safety parameters***

The AEs recorded throughout the study will be pooled in the frequency tables for severity and relationship with the study drug.

### ***Data presentation***

Descriptive statistics will be given for each continuous/discrete variable tested. Numerical data will be presented as mean value, standard deviation, and maximum and minimum values.

Extreme values (outliers) will be analyzed additionally. The data will be pooled according to visits. Categorical variables will be presented as per-visit frequency tables.

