**Statistical criteria**

All statistical calculations will be made using two groups of statistical criteria:

- parametric - to evaluate continuous and interval random values;
- non-parametric – to obtain:
  - evaluations on equality/inequality of proportions of the patients upon their comparison for various visits,
  - analysis of frequencies of the features compared,
 and
  - to evaluate continuous and interval random values in case of non-compliance with normal random distribution.

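### Numerical secondary outcomes tested by Mann-Whitney are to be summarised by mean, SD, maximum and minimum, with no median, quartiles or between-arm estimate that matches the rank test

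*Combined protocol and SAP*

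**What the plan says.** Data presentation covers every variable tested: "Descriptive statistics will be given for each continuous/discrete variable tested". It then gives a single list: "Numerical data will be presented as mean value, standard deviation, and maximum and minimum values". The list makes no exception for skewed data. The next sentence adds: "Extreme values (outliers) will be analyzed additionally". It does not say how.

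The choice of test, by contrast, depends on the distribution. Parametric criteria requires a Kolmogorov-Smirnov check first. Statistical criteria lists as one use of non-parametric methods: "to evaluate continuous and interval random values in case of non-compliance with normal random distribution". Non-parametric tests, item 1, names the two-arm comparison: "To evaluate difference in continuous variables obtained in two different (independent) groups – Mann-Whitney test".

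There is a second route for non-normal data in Parametric criteria, item 5: "In case of abnormal data distribution generalized linear models and/or mixed linear models will be used". No rule says which route applies to which outcome. The statistical sections name no median, quartile, Hodges-Lehmann estimate or between-arm confidence interval.

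**The concern.** The plan lets the distribution decide the test but not the summary. Mean, SD, maximum and minimum are sensitive to skew and extreme values. Mann-Whitney depends on how often a patient in one arm exceeds a patient in the other. If a report pairs mean (SD) by arm with a Mann-Whitney p-value, the reader takes the effect size from two means that the p-value does not address. That size can mislead, and occasionally the direction can too.

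The outcomes exposed are numerical items in Secondary Outcome Measures: cytokine concentrations, induced and spontaneous interferon production, cell counts and, less certainly, durations, symptom scores and area under the curve.

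**Working it through.** **Inputs.** From the documents: 79 evaluable patients per arm (Number of patients) and two-sided testing at 5% (Evaluation of sample size). Assumed: the outcome distributions, because the documents give none. No figure in the plan bears on this point, so there is none to reproduce first.

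**Step 1: how far the mean sits from the typical patient.** For log-normal data with log-SD s, mean/median = exp(s²/2), the share of patients below the mean = Φ(s/2), and SD/mean = √(exp(s²) − 1).

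| s | Mean/median | Below the mean | SD/mean |
|---|---|---|---|
| 1.0 | exp(0.5) = 1.65 | Φ(0.5) = 69% | √(e − 1) = 1.31 |
| 2.0 | exp(2) = 7.39 | Φ(1) = 84% | √(e⁴ − 1) = 7.32 |

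**Step 2: how often direction conflicts, equal spread.** 4,000 simulated trials per setting, 79 per arm, true median ratio 1.3-2.0. Counted: trials where Mann-Whitney is significant and the difference in means has the opposite sign, as a share of significant results.

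| Log-SD, both arms | Opposite sign among significant results |
|---|---|
| 1.0 | 0-0.9% |
| 1.5 | 1.7-5.5% |
| 2.0 | 7.3-13.7% |

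Repeat runs move these by about a percentage point. As a share of all trials, conflict occurs in 0.1-4.5% for log-SD 1-2, and in none at log-SD 0.5.

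**Step 3: unequal spread.** One arm has log-SD 1.0 and a median 1.5 times that of the other arm.

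- Other arm log-SD 1.6: 69-70% of significant results conflict. About 46% of trials are significant, so 0.46 × 0.70 ≈ 32% of all trials conflict. The true means are 1.5 × exp(0.5) = 2.47 against exp(1.28) = 3.60, so this setting puts means and medians in opposite order from the start.
- Other arm log-SD 1.2: 8% of significant results, 5% of all trials. The true means are 2.47 against exp(0.72) = 2.05, in the same order as the medians.

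**Step 4: a bounded outcome, constructed to show the mechanism.** Days of fever, 79 per arm. Control: 60 patients at 3 days, 19 at 4. Test: 57 at 2 days, 22 at 7.

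- Means: (60×3 + 19×4)/79 = 256/79 = 3.24 (SD 0.43) against (57×2 + 22×7)/79 = 268/79 = 3.39 (SD 2.26). The test arm looks slightly worse.
- Mann-Whitney: a test patient has the longer fever in 22/79 = 28% of pairs; p = 3.7 × 10⁻⁷ in favour of the test arm.
- Medians: 3 against 2 days, agreeing with the test.
- Hodges-Lehmann: of 79 × 79 = 6,241 pairwise differences (test minus control), 57×19 = 1,083 equal −2, 57×60 = 3,420 equal −1, and 1,738 are positive. The middle (3,121st) difference is −1 day, agreeing with the test.

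This shows that conflict is possible on a 7-day scale, not that it is likely.

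**Step 5: does the proposed estimate behave?** In the log-normal simulations, unequal spread included, the Hodges-Lehmann estimate never disagreed in sign with a significant Mann-Whitney result.

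**The case against.** Four objections have weight.

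- **Rank tests are not the fixed route.** Parametric criteria, items 5 and 6, allow generalized linear or mixed models with the distribution chosen by AIC, and Mann-Whitney appears in a list of potential comparisons. This stands. A reader might infer that no between-arm difference could be stated for any of these outcomes, but a model can supply one. The point is limited to outcomes actually analysed by ranks.
- **The high conflict rates come from chosen scenarios.** This stands. A reader might infer from the 69-70% figure that the means would usually contradict the test. The documents give no reason to expect so large a difference in spread; equal or mildly unequal spread gives about 0-14%.
- **Log-normal tails do not suit most of the list.** This stands for scores and durations: the fever score runs from 0 to 3 and observation lasts 7 days. The simulations speak mainly to the immune parameters. For those, Study design leaves blood sampling to the investigator's discretion, so 79 per arm is not assured.
- **Other parts of the plan may cover it.** The extra outlier analysis has no stated content, and skew is not only a matter of outliers. Survival analysis could yield medians for durations, but the plan does not assign it to them. The short list of summaries may not be meant to exclude others, yet it is the only rule written down.

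One technical objection carries part of the way. With unequal spread the arms do not differ by a simple shift, so the Hodges-Lehmann value is then the median pairwise difference and not a shift parameter. It still belongs with the test, as step 5 shows.

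**Conclusion.** The point holds as a reporting weakness that should be corrected. For numerical secondary outcomes analysed by Mann-Whitney, the only planned summary does not match the test, and no between-arm estimate with an interval accompanies the p-value. This mismatch follows from the text alone.

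The size of its effect rests on assumed log-normal data with 79 per arm: opposite direction in about 0-14% of significant results under equal spread, and more only with marked differences in spread or skew. Even without a reversal, at log-SD 1.0-2.0 the reported mean would be 1.6 to 7.4 times the median.

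A reader might go further and doubt the main conclusion. The documents do not support that: the primary outcome is a proportion and the non-inferiority hypothesis rests on it, so alpha, power and sample size do not change.

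**What to change.** In Data presentation, keep mean and SD (with maximum and minimum) for all numerical outcomes. Add that every outcome analysed by a rank test will also be presented with median and quartiles by arm, and with the Hodges-Lehmann between-arm difference and its 95% confidence interval. For right-skewed concentrations, a geometric mean ratio with its interval is an optional addition.

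The cost is a sentence or two in the SAP and a few extra table columns. UNIVARIATE and NPAR1WAY, both already listed in the plan, supply the output. No new data are needed and the design does not change.
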